4.5.2. Immunogenicity Variables

Assays to determine serum levels of hepatitis E antibodies (IgG and IgM) will be performed at Emory's VTEU laboratory. Venous blood samples (approximately 10 mL) for antibody assays will be collected from each subject at screening and sent directly to Emory's VTEU laboratory for baseline testing. Seronegative samples will be defined as per the Wantai HEV-IgM and IgG ELISA package inserts (A/C.O. <0.9).

Venous blood samples (approximately 10 mL) will be collected immediately prior to each study vaccination (Days 1, 29, and 180) and Days 8, 15, after each study vaccination (Days 8, 15, 36, 43, 187, 194), Day 29 after each boost vaccination (Days 57 and 208), and Day 360. Subjects who withdraw early will have hepatitis E antibody assays run on available sera. Samples for immunogenicity assessments will be shipped from the DMID CMS to Emory's VTEU laboratory for vaccine immunogenicity assessments beginning with the completion of the Day 360 visit.

Seroconversion will be defined as a change from a seronegative result to a seropositive result as defined by the Wantai HEV-IgM and IgG ELISA package inserts (A/C.O. >1.1). As defined by prior studies,²⁴ the antibody concentration in samples negative for hepatitis E virus IgG was set at 0.0385 Wu/mL which was half the lower limit of quantification. A 4-fold seroconversion will be defined as a HEV IgG \geq 0.154 in a subject that was HEV seronegative at Day 1.

Immunogenicity will be assessed by serum immune responses:

• Serum will be separated from blood samples collected on Days 1, 8, 15, 29, 36, 43, 57, 180, 187, 194, 208, and 360 and HEV IgG and IgM will be determined by ELISA.

5. SAMPLE SIZE CONSIDERATIONS

The sample size for this study was selected to obtain preliminary estimates of HEV-239 vaccine safety and immunogenicity in a time sensitive manner.

Given an N of 20 vaccinees, there is an \sim 88% probability of detecting an adverse event occurring in 10% of the population and a \sim 99% probability of detecting an adverse event occurring in 20%. Placebo subjects are included in order to reduce observer bias and are not intended to be a comparison group. Probabilities of observing at least one adverse event for a given true event rate are presented in the Table 2.

6. GENERAL STATISTICAL CONSIDERATIONS

6.1. General Principles

All continuous variables will be summarized using the following descriptive statistics: n (non-missing sample size), mean, standard deviation, median, maximum and minimum. The frequency and percentages (based on the non-missing sample size) of observed levels will be reported for all categorical measures. In general, all data will be listed, sorted by treatment and subject, and when appropriate by visit number within subject. All summary tables will be structured with a column for each treatment in the order HEV-239, Placebo and will be annotated with the total population size relevant to that table/treatment, including any missing observations.

6.2. Timing of Analyses

The final analysis will be performed after database lock. No interim analysis is planned.

6.3. Analysis Populations

6.3.1. Modified Intention-to-Treat (mITT) Population

The modified intent-to-treat (mITT) population includes all subjects who received at least one study vaccination and contributed both pre- and at least one post-study vaccination blood sample for immunogenicity testing for which valid results were reported. Subjects will be analyzed according to the study arm to which they were randomized.

6.3.2. Per Protocol Population

The per protocol (PP) population includes all subjects in the mITT subset with the following exclusions:

- Data from all available visits for subjects found to be ineligible at baseline.
- Data from all visits subsequent to major protocol deviations, such as:
 - Second or third study vaccination not received,
 - Receipt of non-study licensed live vaccine within 30 days prior to or after each study vaccination,
 - Receipt of non-study licensed inactivated vaccine within 14 days prior to or after each study vaccination,
 - Receipt of immunosuppressive therapy (e.g., corticosteroids) within 30 days prior to or after each study vaccination.
- Data from any visit that occurs substantially out of window.
- In the case of mis-randomization, subjects will be analyzed according to the study product received.

6.3.3. Safety Population

The Safety Analysis population includes all subjects who received at least one study vaccination.

6.4. Covariates and Subgroups

The protocol does not define any formal subgroup analyses, and the study is not adequately powered to perform subgroup analyses.

6.5. Missing Data

All attempts will be made to collect all data per protocol. As missing data are expected to be minimal, no imputation will be performed for missing values. Any data point that appears to be erroneous or inexplicable based on clinical judgment will be investigated as a possible outlier. If data points are identified as outliers, sensitivity analyses will be performed to examine the impact of including or excluding the outliers. Any substantive differences in these analyses will be reported.

6.6. Interim Analyses and Data Monitoring

Safety Review

The Safety Monitoring Committee (SMC) will review study progress and subject clinical, safety, and reactogenicity data at the following time points:

- The SMC will be provided with top line safety data through Day 57 for all participants.
- Final review meeting: 6 to 8 months after clinical database lock to review the cumulative unblinded safety and efficacy data for this trial. The data will be provided in a standard summary format. The SMC may be asked to provide recommendations in response to questions posed by DMID.
- Ad hoc when a halting rule is met, for immediate concerns regarding observations during this trial, or as needed.

Study Halting Criteria

Further enrollment and study vaccinations will be halted for SMC review/recommendation if any of the following are reported:

- Any subject experiences ulceration, abscess, or necrosis at the injection site related to study vaccination.
- Two or more subjects who have received at least one dose of study vaccine to date experience the same, at Medical Dictionary for Regulatory Activities (MedDRA) preferred term (PT) level, severe (grade 3) study vaccine-related unsolicited adverse event.
- Two or more subjects who have received at least one dose of study vaccine to date experience a severe (grade 3) study vaccine-related laboratory adverse event in the same laboratory parameter.
- Two or more subjects who have received at least one dose of study vaccine to date experience the same severe (grade 3) solicited injection site adverse event that persists for 3 or more days and does not resolve or decrease to a lower grade (The size [measured in mm] of ecchymosis, erythema and induration/swelling will not be used as a halting criterion).
- Two or more subjects who have received at least one dose of study vaccine to date experience the same severe (grade 3) study vaccine-related solicited systemic adverse event that persists for 3 or more days and does not resolve or decrease to a lower grade (Subjective systemic reaction corroborated by study personnel).
- Any subject experiences a study vaccine-related laryngospasm, bronchospasm, or anaphylaxis within 1 day of study vaccination.
- Any subject experiences a study vaccine-related allergic reaction (e.g., generalized urticaria) within 3 days of study vaccination.

• Any subject experiences a study vaccine-related SAE from the time of the first study vaccination through the subject's last study visit.

Individual Halting Criteria

Individual subjects will not be administered boost vaccination doses (2nd or 3rd vaccination) if he or she experiences ANY of the following:

- Anaphylaxis within 1 day after administration of a study vaccine.
- Allergic reaction (e.g., generalized urticaria) within 3 days after administration of a study vaccine.
- A serious adverse event (SAE) that is considered to be study vaccine-related.
- A severe (grade 3) laboratory adverse event that is considered to be study vaccine-related and persists for 3 or more days.
- A severe (grade 3) unsolicited adverse event that is considered to be study vaccine-related and does not resolve or decrease to a lower grade.

These interim analyses will not involve testing of a hypothesis. In no case will the trial be prematurely terminated based on testing a hypothesis concerning the outcomes of interest.

6.7. Multicenter Studies

Not applicable. This study will take place at a single Vaccine Treatment and Evaluation Unit (VTEU).

6.8. Multiple Comparisons/Multiplicity

This study was not designed to test any specific null hypothesis, and as such no adjustments for multiple testing are planned.

7. STUDY SUBJECTS

7.1. Disposition of Subjects

Table 11 presents a summary of the reasons that subjects were screened but not enrolled.

The composition of analysis populations, including reasons for subject exclusion, by treatment arm, is presented in Table 9. Excluded subjects are listed in Listing 4.

The disposition of subjects in the study will be tabulated by treatment group (Table 8). The table shows the total number of subjects screened, enrolled, receiving at least 1 dose, receiving at least 2 doses, discontinued dosing or terminated from study follow-up and the number completing the study.

A flowchart showing the disposition of study subjects, adapted from the Consort Statement [12] will be included (Figure 2). This figure will present the number of subjects screened, enrolled, lost to follow-up, and analyzed, by treatment arm.

A listing of subjects who discontinued dosing or terminated from study follow-up and the reason will be included in Listing 1.

7.2. **Protocol Deviations**

A summary of subject-specific protocol deviations will be presented by the reason for the deviation, the deviation category, and treatment group for all subjects (Table 3). Deviations that are considered major deviations that will be reviewed for possible subject exclusion from the per protocol population include: second or third study vaccination not received, receipt of non-study licensed live vaccine within 30 days prior to or after a study vaccination, and receipt of non-study licensed inactivated vaccine within 14 days prior to or after a study vaccination. All subject-specific protocol deviations and non-subject specific protocol deviations will be included as data listings (Listing 2 and Listing 3, respectively).

8. IMMUNOGENICITY EVALUATION

All immunogenicity variables will be listed by treatment group, subject, and visit (Listing 7). N, Geometric Mean, Standard Deviation, Minimum and Maximum will summarize continuous immunogenicity variables, whereas number and percent will summarize categorical immunogenicity variables. This study was not designed to test a specific null hypothesis, rather the primary objectives included assessing the safety and immunogenicity of HEV-239 vaccine administered via intramuscular injection.

Immunogenicity data summaries and analysis will be presented for the mITT and PP populations.

Immune response will be presented graphically using reverse cumulative distribution (RCD) curves (Figure 3, Figure 4, Figure 5, and Figure 6), and longitudinal presentation of GMCs (Figure 7, Figure 8, Figure 9, and Figure 10).

8.1. Primary Immunogenicity Analysis

HEV IgG by ELISA

The number and percentage of subjects showing \geq 4-fold rise from the baseline in serum HEV IgG concentration determined by ELISA will be presented with exact (Clopper-Pearson) two-sided 95% CI by study arm at Days 8, 15, 29, 36, 43, 57, 180, 187, 194, 208, and 360 (Table 19 and Table 20).

8.2. Secondary Immunogenicity Analyses

HEV IgG by ELISA

The number and percentage of subjects with seroconversion (defined as crossing the threshold from negative to positive) from baseline in serum HEV IgG determined by ELISA will be presented with exact (Clopper-Pearson) two-sided 95% CI by study arm at Days 8, 15, 29, 36, 43, 57, 180, 187, 194, 208, and 360 (Table 23 and Table 24). GMCs and corresponding 95% confidence intervals will be reported (Table 15 and Table 16).

HEV IgM by ELISA

The number and percentage of subjects with seroconversion (defined as crossing the threshold from negative to positive) from baseline in serum HEV IgM determined by ELISA will be presented with exact (Clopper-Pearson) two-sided 95% CI by study arm at Days 8, 15, 29, 36, 43, 57, 180, 187, 194, 208, and 360 (Table 21 and Table 22). GMCs and corresponding 95% confidence intervals will be reported (Table 17 and Table 18).

8.3. Exploratory Immunogenicity Analyses

Not applicable.

9. SAFETY EVALUATION

Safety listings will be sorted by treatment group, subject, and timepoint. N, Mean, Standard Deviation, Minimum and Maximum will summarize continuous safety variables, whereas number and percent will summarize categorical safety variables. Safety data will be summarized for the Safety Analysis Population. Subjects receiving a vaccination according to a study arm other than the study arm to which they were randomized, will be analyzed according to the vaccination they actually received.

9.1. Demographic and Other Baseline Characteristics

Summaries of age, sex, ethnicity, and race will be presented by treatment group and overall (Table 12 and Table 13). Ethnicity is categorized as Hispanic or Latino, or not Hispanic and not Latino. In accordance with National Institutes of Health (NIH) reporting policy, subjects may self-designate as belonging to more than one race or may refuse to identify a race, the latter reflected in the eCRF as "No" to each racial option.

Individual subject listings (Appendix 3) will be presented for all demographics (Listing 5); pre-existing medical conditions (Listing 6); vital signs and oral temperature (Listing 13); and concomitant medications (Listing 15).

9.1.1. Prior and Concurrent Medical Conditions

All current illnesses and past pre-existing medical conditions will be MedDRA® coded using MedDRA dictionary version 22.0 or higher.

Summaries of subjects' pre-existing medical conditions will be presented by treatment group (Table 14).

Individual subject listings will be presented for all medical conditions (Listing 6).

9.1.2. Prior and Concomitant Medications

Summaries of medications that were started prior to dosing and continuing at the time of dosing will be presented by WHO Drug Terms 2 and 3 and treatment group (Table 78).

Individual subject listings will be presented for all concomitant medications (Listing 15).

9.2. Measurements of Treatment Compliance

The number of doses of study product administered to subjects will be presented by treatment group as part of the subject disposition table (Table 8).

Table 10 presents the number of subjects who received first dose, by treatment arm.

9.3. Adverse Events

When calculating the incidence of adverse events (i.e., on a per subject basis), each subject will only be counted once and any repetitions of adverse events within a subject will be ignored; the denominator will be the total number of subjects in the safety population or the number of subjects in the safety population who received a given dose, first dose, second dose, or third dose as appropriate. All adverse events reported will be included in the summaries and analyses.

An overall summary of adverse events is presented in Table 25.

9.3.1. Solicited Events and Symptoms

Systemic solicited adverse events were collected pre-vaccination, and systemic and local solicited adverse events were collected 30 minutes post-vaccination and then daily for 7 days after each vaccination and graded on a scale of 0 (absent), 1 (mild), 2 (moderate) and 3 (severe). The grading scales are presented in Table 4 and Table 5. Systemic events include: arthralgia, fever, feverishness, fatigue, headache, malaise, myalgia, nausea, and vomiting. Local events include: ecchymosis severity and measurement, erythema measurement, induration/swelling severity and measurement, pain, pruritus, and tenderness.

The proportion of subjects reporting at least one solicited adverse event will be summarized for each solicited adverse event, any systemic symptom, any local symptom, and any symptoms. The 95% confidence interval (CI) calculated using Clopper-Pearson methodology from a binomial distribution (SAS Proc Freq with a binomial option) will be presented (Table 27).

For each systemic and local event, any systemic event, any local event, and any solicited event, the maximum severity over 7 days after each vaccination will be summarized for the Safety population. The number and percentage of subjects reporting each event will be summarized by the maximum severity and treatment group, separately for each vaccination and over all vaccinations. For each event the denominator is the number of subjects with non-missing data for the specific event (Table 28).

The number of subjects reporting a solicited adverse event will be summarized for each day post vaccination for each vaccination and for all vaccinations combined both in a summary table (Table 29, Table 30, Table 31, Table 32, Table 33, Table 34, Table 35, and Table 36) and graphically in a bar chart (Figure 11, Figure 12, Figure 13, Figure 14, Figure 15, Figure 16, Figure 17, and Figure 18). A comparison of the event rate for each treatment group between vaccination 1 and vaccination 3 will be presented (Table 37). The duration of solicited adverse events will be summarized by dose number and treatment group (Table 38).

Solicited adverse events by subject will be presented in Listing 8 and Listing 9.

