6.2 Enrollment/Baseline: Visit 01, Day 1, Vaccination Clinic Visit (All Groups)

The investigator should ensure that all enrollment criteria have been met during screening. If a subject's status (including any unscheduled laboratory results or the receipt of additional medical records) after screening but before the prime vaccination changes such that the subject no longer meets all enrollment criteria, then the subject should be excluded from participation in the study.

If the initial laboratory screening occurred more than 28 days before baseline (Day 1) but the subject was unable to be vaccinated within the 28-day window (e.g., due to meeting **Exclusion Criteria** in **Section 5.1.2** or for other reasons), the subject must have safety laboratories repeated (see protocol-specific MOP for details about laboratories).

Prior to Vaccination

- Review inclusion and exclusion criteria to ensure the subject remains eligible for enrollment
- Review medical history for any interval changes
- Review prestudy and concomitant medications
- Obtain vital signs (HR, BP, and oral temperature)
- Subjects who have a diastolic blood pressure value >90 mmHg or a systolic blood pressure value >140 mmHg prior to the prime vaccination can receive the vaccination if the elevated blood pressure is considered to be not clinically significant and the subject had acceptable blood pressure at screening.

- Perform symptom-directed PE (if needed).
- Perform urine pregnancy test for women of childbearing potential within 24 hours prior to immunization. Test result must be known and negative prior to vaccination.
- Review of birth control history with female subjects
- Counsel subjects to use adequate birth control methods to avoid pregnancy
- Subjects will be enrolled in Advantage eClinical[®] and randomly assigned to a Study Group (see Section 10.3.1 Randomization Procedures for details).
- Obtain serum for immunogenicity assays.
- Collect PBMCs and plasma for future assays.
- Study vaccine will be prepared on-site by an unblinded site research pharmacist (see Section 4.3).
- Pre-administration reactogenicity assessments will be performed prior to the first study vaccination to establish baseline. A subject with mild pre-administration reactogenicity which is transient, resolving, or clinically insignificant may receive vaccination at the investigator's discretion.

Vaccination

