6.3.1.10 Visit 11, Day 180 +/- 14 Days from Prime Vaccination; Clinic Visit

Prior to Vaccination

- Review medical history for any interval changes
- Review concomitant medications
- Obtain vital signs (HR, BP, and oral temperature)
- Subjects who have a diastolic blood pressure value >90 mmHg or a systolic blood pressure value >140 mmHg prior to the prime vaccination can receive the vaccination if the elevated blood pressure is considered to be not clinically significant and the subject had acceptable blood pressure at screening.
- Perform symptom-directed PE (if needed).
- Perform urine pregnancy test for women of childbearing potential within 24 hours prior to immunization. Test result must be known and negative prior to vaccination.
- Review of birth control history with female subjects.

DMID/NIAID/NIH

- Counsel subjects to use adequate birth control methods to avoid pregnancy.
- Obtain blood for safety laboratories (Section 2.3.1).
- Obtain serum for immunogenicity assays.
- Collect PBMCs and plasma for future assays
- Review inclusion and exclusion criteria to ensure the subject remains eligible for boost vaccination
- Study vaccine will be prepared on-site by an unblinded site research pharmacist (see Section 4.3).
- Pre-administration reactogenicity assessments will be performed prior to vaccination to establish baseline. A subject with mild pre-administration reactogenicity which is transient, resolving, or clinically insignificant may receive vaccination at the investigator's discretion.

Vaccination

- The unblinded study vaccine administrator will vaccinate the subject according to vaccination assignment in the subject's preferred arm.
- Following receipt of study product, subjects may have the injection site covered with an adhesive bandage (e.g. BAND-AID®) as needed.

Following Vaccination

- Observe subjects for a minimum of 30 minutes following immunization.

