8.1 Assessing and Recording Safety Parameters

8.1.1 Adverse Events (AEs)

ICH E6 defines an AE as any untoward medical occurrence in a patient or clinical investigation subject administered a pharmaceutical product regardless of its causal relationship to the study treatment. FDA defines an AE as any untoward medical occurrence associated with the use of a drug in humans, whether or not considered drug related.

An AE can therefore be any unfavorable and unintended sign (including an abnormal laboratory finding), symptom, or disease temporally associated with the use of medicinal (investigational) product. The occurrence of an AE may come to the attention of study personnel during study

DMID/NIAID/NIH

visits and interviews of a study recipient presenting for medical care, or upon review by a study monitor.

All AEs, including solicited local (injection site) and systemic (subjective and quantitative) reactions, will be captured on the appropriate data collection form and eCRF. Information to be collected for AEs includes event description, date of onset, assessment of severity, relationship to study product and alternate etiology (assessed only by those with the training and authority to make a diagnosis and listed on the Form FDA 1572 as an investigator), date of resolution, seriousness and outcome. AEs occurring during the trial collection and reporting period will be documented appropriately regardless of relationship. AEs will be followed through resolution.

Any medical condition that is present at the time that the subject is screened will be considered as baseline and not reported as an AE. However, if the severity of any pre-existing medical condition increases, it should be recorded as an AE.

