3.2. Endpoints

3.2.1. Primary

- Determine the number of solicited local and systemic reactogenicity events from the time of study vaccination through Day 8 after each study vaccination.
- Determine the number of vaccine-related unsolicited adverse events (AE) from the time of each study vaccination through Day 29 after each study vaccination.
- Determine the number of clinical safety laboratory AEs at Day 8 after each study vaccination.
- Determine the number of vaccine-related serious adverse event (SAE) from the time of first study vaccination through 6 months after the last dose of vaccine.
- Determine the number of subjects showing ≥4-fold rise in serum HEV IgG concentration by Enzymelinked Immunosorbent Assay (ELISA) from the baseline at Days 8, 15, 29, 36, 43, 57, 180, 187, 194, 208, and 360.

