4.2. Discussion of Study Design, Including the Choice of Control Groups

This study is designed to determine the safety and immunogenicity of HEV-239 administered via intramuscular injection. Five placebo subjects are included in order to reduce observer bias and are not intended to be a comparison group.

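### The summary reactogenicity tables count any systemic symptom after a dose without reference to that subject's pre-dose grade, so they cannot separate new or worsened symptoms from those already present.

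*SAP*

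**What the plan says.** **Collection.** SAP 9.3.1 states: "Systemic solicited adverse events were collected pre-vaccination, and systemic and local solicited adverse events were collected 30 minutes post-vaccination". The grades run from 0 to 3. The protocol gives the purpose; for the third dose (6.3.1.10) it reads "Pre-administration reactogenicity assessments will be performed prior to vaccination to establish baseline", and Sections 6.2 and 6.3.1.4 provide the same for doses 1 and 2. At all three visits dosing may go ahead at the investigator's discretion despite mild symptoms: "A subject with mild pre-administration reactogenicity which is transient, resolving, or clinically insignificant may receive vaccination".

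**Endpoint.** The first primary endpoint (SAP 3.2.1, matching Protocol 3.3.1) is: "Determine the number of solicited local and systemic reactogenicity events from the time of study vaccination through Day 8 after each study vaccination". It does not mention the pre-dose grade.

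**Analysis.** SAP Table 27 counts subjects who report an event at least once. For Table 28, "the maximum severity over 7 days after each vaccination will be summarized for the Safety population"; the table's footnote confirms that only post-dose grades enter. Table 25 counts subjects with one or more systemic solicited events, and Table 37 splits subjects at mild or greater. None of these refers to the pre-dose grade. SAP 3.3 defines baseline once, before the first dose, so no per-dose baseline exists for doses 2 and 3.

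**Where the pre-dose grade does appear.** The by-day shells, Tables 29 to 36, have a Pre-Dose column by symptom and grade. Listing 8 gives systemic symptoms by subject, dose and day, including clinic-collected data.

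**The concern.** A subject with a mild headache before the injection and the same mild headache that evening enters Tables 25, 27 and 28 as having a solicited systemic event for that dose, and crosses the mild-or-greater line in Table 37. Nothing else in the summary tables separates that subject from one whose headache started after the dose:

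- Protocol 8.2 exempts Grade 1 and 2 solicited events from relatedness assessment, and Listing 8 records an alternate etiology for Grade 3 events only.
- The five placebo subjects "are not intended to be a comparison group", so no contrast between arms is planned that would remove background symptoms.
- The Pre-Dose column in Tables 29 to 36 is a group count. It does not link one subject's grades before and after the dose.

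At stake is how the per-dose systemic rates are read. Headache, fatigue, myalgia and nausea are common without vaccination, and the pre-dose assessment is the subject-level control that the trial collects for them. The summary tables make no use of it.

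**Working it through.** **Plan's own figure.** The plan gives no figure for this point. Its only related numbers are the detection probabilities for 20 vaccinees (Protocol 10.2, SAP Table 2). With 1 − (1 − p)^20 they reproduce exactly: 0.20, 1.98, 18.21, 87.84 and 98.85% for p = 0.01, 0.1, 1, 10 and 20%. They are not in dispute.

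**One subject.** With 20 vaccinees, one added subject is 1/20 = 5 points. For example, 2/20 = 10% (exact 95% CI 1.2 to 31.7) becomes 3/20 = 15% (3.2 to 37.9). If that subject would also have had a new event, nothing is added, hence *up to* 5 points.

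**Expected excess.** Let p be the true rate per dose of new or worsened systemic events, and b the chance per dose that a subject has a mild pre-dose symptom that persists unchanged. Both are assumptions; neither is in the documents. Taking them as independent of each other and across doses:

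- Rate shown per dose = 1 − (1 − p)(1 − b); excess = b(1 − p).
- Rate shown after any of three doses = 1 − [(1 − p)(1 − b)]^3.
- True any-dose rate = 1 − (1 − p)^3.

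With p = 10%, the true rates are 10.0% per dose and 1 − 0.9^3 = 27.1% after any dose.

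| b | Shown per dose | Excess (points) | Shown any dose | Excess (points) |
|---|---|---|---|---|
| 2% | 11.8% | 1.8 | 31.4% | 4.3 |
| 5% | 14.5% | 4.5 | 37.5% | 10.4 |
| 10% | 19.0% | 9.0 | 46.9% | 19.8 |

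For b = 5%: 1 − 0.90 × 0.95 = 14.5%, and 1 − 0.855^3 = 37.5%.

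**Sensitivity to p.** At b = 5%, the excess per dose and after any dose is 4.8 and 12.2 points for p = 5%, and 4.0 and 7.3 points for p = 20%.

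**Chance that it arises at all.** The probability of at least one such vaccinee per dose is 1 − (1 − b)^20 = 33%, 64% or 88% for b = 2%, 5% or 10%.

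**Which values of b are plausible.** Fever or other acute illness in the 3 days before the first dose excludes a subject (Protocol 5.1.2). Fever or moderate to severe acute illness may defer a boost (5.2). Dosing with symptoms is discretionary and confined to mild ones that are transient, resolving or clinically insignificant. These rules favour the lower end of the range.

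**The case against.** The strongest objection is that the SAP does what the protocol asks. The endpoint runs from vaccination through Day 8, and Protocol 10.5.2 calls for subjects reporting each event and for maximum severity, with no condition on the pre-dose grade. The tables are therefore all-causality counts, and over-reporting is the cautious direction in a descriptive Phase 1 study with no hypothesis test. This stands: the all-events rows are legitimate and should remain the main presentation.

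Four stronger readings are tempting, and the documents do not support them.

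- *The tables contradict the protocol's own AE rule.* Protocol 8.1.1 does say "However, if the severity of any pre-existing medical condition increases, it should be recorded as an AE". But that rule concerns medical conditions present at screening, not a passing symptom noted just before a dose. It does not govern here.
- *The pre-dose data go unused.* Tables 29 to 36 print them. Listing 8 probably lets them be compared case by case: its shell has no explicit pre-dose row, but SAP 4.5 says that all recorded data are listed. With 25 subjects that is workable, though it yields no summary rate.
- *These subjects are counted wrongly.* That presumes a causal definition of a solicited event, which the plan never adopts.
- *The any-dose excess is 6, 14 or 27 points.* Those figures are 1 − (1 − b)^3 for b = 2%, 5% and 10%. They hold only if no affected subject would otherwise report a systemic event, so they are upper bounds.

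One further objection also stands. A bare new-or-higher-grade rule would drop a mild pre-dose headache that resolves and returns at the same grade on a later day. As the headline, such a rule could understate reactions.

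**Conclusion.** The point holds as a gap in the summaries, not as an error in the endpoint. Tables 25, 27, 28 and the systemic panel of Table 37 cannot distinguish systemic symptoms that began or worsened after a dose from those already present, although a per-dose baseline is collected. The effect can only be upward. It falls mainly in the mild grade, because dosing with symptoms is permitted only when they are mild. It concerns systemic events, since the SAP collects only those before vaccination.

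The size is uncertain. The firm figure is up to 5 points per affected vaccinee. The ranges of 1.8 to 9.0 points per dose and 4.3 to 19.8 points after any dose rest on assumed persistence of 2% to 10%, an assumed 10% true rate and independence across doses. Few subjects may in fact be affected.

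**What to change.** In SAP 9.3.1:

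1. Define the pre-dose assessment of each dose as the baseline for systemic solicited events after that dose.
2. Keep the all-events rows as the main presentation.
3. Add supplementary rows to Tables 27 and 28 and to the systemic panel of Table 37 for events new or worsened after that dose, with exact confidence intervals in Table 27.
4. Count an event as new or worsened if it was absent pre-dose, is of higher grade than pre-dose, or recurs after a symptom-free day. Leave out only symptoms present continuously since the pre-dose assessment at the same or a lower grade.

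The cost is SAP wording, one derived flag per subject, symptom and dose from data already collected, and longer tables. Trial conduct does not change. The added rows will miss some true reactions masked by a same-grade pre-dose symptom, which is why the all-events rows stay beside them.
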